3. TRIAL DESIGN

The design of the proposed main trial work has been developed with reference to CONSORT (http://www.equator-network.org/reporting-guidelines/consort/) and SPIRIT guidelines (http://www.spirit-statement.org/), and the TIDieR checklist and guide (http://www.bmj.com/content/348/bmj.g1687).

MAIN TRIAL

Our trial will be a multicentre rater-blinded (primary outcome) RCT with 2 parallel arms. It will compare a psychological intervention (CBT_{BAR}) + TAU (treatment condition) to TAU alone (control condition). The trial will recruit 338 participants who meet the Bipolar At Risk (BAR) criteria and randomly allocate them to a 6-month package of either condition.

Randomisation will be independent and concealed, using permuted stratified blocks, where site (5-levels) and BAR group (3-levels) are the stratification factors. It will be conducted via a web-based system conducted within York CTU. Assessors will be masked to allocated treatment. Masking will be maintained using a wide range of strategies (e.g. separate offices for therapists and researchers, protocols for answering phones, message taking and secretarial support, separate diaries and security for electronic randomisation information).

Assessor's blind and independent to treatment group will collect all outcome and mediational variables at baseline, 17-weeks (during treatment window capturing SCID-5 + PSR's (SCID LIFE), HAPPI, BC and ISS), 27-weeks (after therapy cessation), and at 52-weeks. Participants will receive £20 reimbursement upon completion at each assessment point as a thank you for their time.

The assessors will also contact people via phone at 39-weeks to promote retention in the trial. We will ask about general wellbeing since the last assessment (including documenting any potential serious adverse events), and any changes to contact details. Participants will receive a £5 supermarket voucher of their choice to thank them for their continued participation.

For those participants who are randomly selected to receive the CBT_{BAR}, they will be offered up to 26 individual weekly therapy sessions of up to 60 mins in length. These will be delivered by a Clinical Psychologist or psychological therapist.

NESTED QUALITATIVE WORK

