Following the recruitment process, baseline assessment and randomisation, follow-up assessment points will be at 17-, 27-, and 52-weeks post-randomisation (see "Schedule of Events" in the Appendices (#2)). We will also contact people via telephone at 39-weeks to promote retention in the trial and ask about general wellbeing since the last assessment (including documenting any potential serious adverse events, and any changes to contact details). Assessments will be conducted by research assistants blind and independent to treatment group and will employ both a semi-structured interview to gather data for the primary outcome (blinded) and secondary outcomes in addition to self-report questionnaires (unblinded data given the participant will be aware of their treatment allocation). The self-report questionnaires will be offered for completion in paper format.

For those participants who are offered the CBT_{BAR} intervention, a measure of therapeutic alliance (California Psychotherapy Alliance Scales / CALPAS) will be administered to both the participant and the therapist for completion after the 4th and 10th sessions. To ensure the participant is able to complete the measure openly, the trial manager (LP) will be responsible for contacting the participant and arranging administration of this measure to prevent the therapist being the person to do this. Additionally, the Facilitative Alliance Measure will be administered by the trial manager (LP) to the research participants following each follow-up appointment with a research assistant. This will measure alliance with the research assistant.

Follow-up visits are typically offered via face-to-face methods utilising outreach principles where participants are seen in non-stigmatising settings. This approach means that people often choose to be seen at home although other least restrictive venues e.g. youth centres, colleges, primary care settings, are also employed. Staff training will be conducted with all staff and regular arrangements for ensuring inter-reliability across sites. Adapting to assessments via phone/virtual calls still retains validity and reliability on our primary outcome [84].

QUALITATIVE RESEARCH

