The control condition is treatment as usual plus follow-up (17-, 27-, and 52- weeks), which represents an enhancement over routine care since symptoms of mania will be detected earlier than in usual practice and appropriate treatment referrals made. We will not be asking referrers to withhold any treatment. Participation in assessments may reduce the (frequently high) number of contacts required in order to receive appropriate treatment for BD. Assessments will identify untreated BD and any risks to self or others that require immediate action. TAU alone will not include liaison with a clinical team, should one be involved, except where risk issues necessitate this. This is a pragmatic approach that will improve generalisability of our findings. As in previous trials we have undertaken, there will be a clear safety protocol to alert clinicians should suicidal or dangerous ideation emerge, and an operational protocol for initiating high quality routine care should conversion occur.

Treatment as usual will include standard psychiatric care, psychological and vocational interventions from a variety of agencies will be available to both treatment and control arms (although, in our experience, provision for this population is poor). Due to diagnostic uncertainty, access to services includes Improving Access to Psychological Therapies (IAPT), CAMHS, primary care, EIT and community mental health teams. CBT_{BAR} differs from standard NHS treatment for young people with mood swings as highlighted in our RfPB trial [59]. All routine or additional treatments in both conditions will be monitored using a Treatment Documentation Sheet and specific treatments (anti-depressant and psychotherapy treatment) monitored within the LIFE assessment tool as important potential confounders.

CONCOMITANT THERAPY

It would be unethical to restrict the therapeutic options of the young people participating. Our approach will, therefore, be primarily to record the use of all other medication and psychological therapies, document details of dosage, and ensure the follow-up of all randomised participants, irrespective of the interventions that they subsequently receive.

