As well as broadly defined 'medical events' including self-harm and worsening of symptoms which were absent or present at baseline, adverse event recording will also include capturing information about the occurrence of non-medical events such as arrest, imprisonment, and violence to others, which may be contributing factors to an AE or may indicate that an AE has occurred. As an example of the latter, a participant's increased drug abuse—an AE—could result in an arrest.

DEFINITION OF SERIOUS ADVERSE EVENTS (SAE's)

Any untoward medical or psychological occurrence that:

- Results in death
- Is life-threatening (NOTE: this refers to an event in which the subject was at risk of death at the time of event; it does not refer to an event which hypothetically might have caused death if it were more severe)
- Requires inpatient hospitalisation or prolongation of existing hospitalisation (We plan to scrutinise any instances of patients being admitted to psychiatric hospital in the period of the therapy. These events are likely to come to the attention of the therapists or assessors)
- Results in persistent or significant disability / incapacity
- Other 'important medical events' may also be considered serious if they jeopardise the participant or require an intervention to prevent one of the above consequences plus any serious violent incidents or formal complaints about the intervention.

NB: Planned hospitalisation for a pre-existing condition, without a serious deterioration in health, is not considered a serious adverse event.

REPORTING PROCEDURES FOR ADVERSE EVENTS

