For the avoidance of doubt, all AE/SAEs should be collected for all trial subjects from the time of their enrolment into the study. The time of enrolment is defined as the time at which, following recruitment, a subject sign and dates the informed consent form. Initially all adverse events should be recorded on the Adverse Events Report Form by whoever has identified the event. This form should then be shared with the Chief Investigator ([name]) or trial manager ([name]) who makes an assessment as to whether the event is defined as serious in consultation with both the definitions in the Protocol and the GMMH SOP (RD2OP41 Recording and Reporting Adverse Events for non-CTIMPS). The response to an adverse incident will be determined on a case-by-case basis and in line with HRA guidance. The recorded AE's will be regularly monitored by the trial management group in line with Good Clinical Practice Guidelines.

REPORTING PROCEDURES FOR SERIOUS ADVERSE EVENTS

A serious adverse event (SAE) occurring to a participant will be reported to the following agencies and committees using the HRA report of serious adverse event form (see HRA website):

- To the sponsor, no later than 3 calendar days from awareness of the event at the site.
- The REC that gave a favourable opinion of the study The DMC who will be responsible for reviewing serious, unexpected and related events
- Additionally, all SAE's will be reported to the responsible clinical team and the TSC.
- Finally, details of all serious and non-serious adverse events will be reported externally to the funder in regular progress reports.

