14. APPENDICES

- 1. BART II Participant Flow Diagram
- 2. Schedule of Events

				Ар	pendi	x 2: S	chedu	le of I	Events											
Procedures			(Day -28 to -1)	Day 0	Intervention 1, week 1	We	Weekly session, ≤26 sessions CBT _{BAR}										Study Visit 1 (week 17)	Study Visit 2 (week 27)	Study Phone call (week 39)	Study Visit 2 (week 52) Study Completion
Signed Consent Form		X																		
Demog	Demographics																			
Assessment of Eligibility Criteria: SCID-5 + PSR's (SCID LIFE), GAF/SOFAS		X																		
Baseline Assessment Completion: ISS, BDI-II, HAPPI, BC, BCSS, MCQ-30, DTQ, RSQ, EQ-5D, WHOQOL (PSQI/PANSAM?)		X																		
Allocation / Randomisation				Χ																
Alliance Interventions	CBT _{BAR} (including sessional measures: ISS, HAPPI, BC)				X	$\begin{array}{c c c c c c c c c c c c c c c c c c c $														
	Treatment As Usual (TAU) Alone (*not a study procedure, TAU provided by clinical team)					•								•						
	Therapist Alliance: CBT _{BAR} only					X			X											
	Research Assistant Alliance	X															X(?)	X(?)		X(?)
Adverse Event Recording					X	X	X	X	X	X	X	X	X	X	X	X	X	X		X
Contact sheet update																			X	
Assessment of Outcome	nent of mechanism: HAPPI, BC, ISS	X															X	X		X
	Mental Health Experiences																	X		X
	Psychological Process Measurement																	X		X
	Quality of Life/Functioning																	X		X
\mathbf{As} of	Service Use Interview																	X		X

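### Adverse-event recording is tied partly to weekly therapy sessions that only the CBT arm has, so any between-arm comparison of adverse events is open to ascertainment bias against CBT

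*Protocol*

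**What the plan says.** **Who records.** Section 7 (reporting procedures for adverse events) requires events to be collected for every participant from consent. On method it says only that "Initially all adverse events should be recorded on the Adverse Events Report Form by whoever has identified the event". In the definition of serious events it says of psychiatric admissions during the therapy period: "These events are likely to come to the attention of the therapists or assessors".

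**When.** In the Appendix 2 schedule, the row headed "Adverse Event Recording" is marked from the first intervention session through the weekly session columns, then at weeks 17, 27 and 52. It is blank at the consent and baseline stage and at the week-39 call. The row is not split by arm.

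**Who has the weekly contacts.** Section 3 says CBT participants are "offered up to 26 individual weekly therapy sessions of up to 60 mins in length". Appendix 2 describes the other arm as "Treatment As Usual (TAU) Alone (*not a study procedure, TAU provided by clinical team", and section 6 says "The control condition is treatment as usual plus follow-up (17-, 27-, and 52- weeks" (the bracket continues in the text).

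**Week 39.** Section 5 (trial assessments) plans a telephone call to participants in both arms at this point, mainly to support retention, and gives it a safety task as well: "including documenting any potential serious adverse events". Section 3 says the same in substance.

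**Use of the counts.** The DMEC monitors adverse-event incidence (section vi), and serious and non-serious events go to the funder in progress reports (section 7). Section 8 sets out no between-arm analysis of harms.

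**The concern.** A trial therapist who sees a participant nearly every week will hear of events that the participant may not mention at a research visit months later. Section 7 counts self-harm and worsening of symptoms as adverse events, and these are natural topics in a therapy session. The TAU arm has no counterpart. Its scheduled recording visits look back over 17 weeks, then 27 − 17 = 10 weeks, then 52 − 27 = 25 weeks.

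If the arms have the same true event rate, more of the CBT arm's events may reach the report form. A table by arm could then suggest harm where there is none, or mask a real reduction in non-serious self-harm. This is a question of data collection more than of analysis. If the form does not show where an event came from, and the visits do not put the same question to both arms, no later analysis plan can separate more events from more opportunities to report them.

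**Working it through.** **1. The plan's own figure.** Section 6 gives 523 sessions attended, 37 participants allocated to CBT and a mean of 14 in the feasibility trial. 523/37 = 14.1, so the mean is reproduced.

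**2. Scheduled recording occasions.** I read the weekly columns of Appendix 2 as standing for every session, up to 26.

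| Period | CBT, maximum | CBT at 14 sessions | TAU |
|---|---|---|---|
| To week 27 | 26 + 2 = 28 | 14 + 2 = 16 | 2 |
| To week 52 | 26 + 3 = 29 | 14 + 3 = 17 | 3 |

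Each arm also has one serious-event call at week 39.

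**3. What this could do to a comparison.** Take equal true rates in the two arms and let:
- *v* = probability that a research visit picks up an event, the same in both arms (assumption);
- *t* = probability that a therapist picks up an event that the visit missed (assumption, 0.9);
- *c* = share of the 27 weeks with a session: 14/27 = 0.52 at the feasibility mean, 26/27 = 0.96 at the maximum.

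Detection is *v* in TAU and *v* + (1 − *v*)·*c*·*t* in CBT, so to week 27:

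apparent ratio = 1 + [(1 − *v*)/*v*]·*c*·*t*

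For example, at *v* = 0.5 and *c* = 26/27: 1 + 1 × 0.963 × 0.9 = 1.87.

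Over 52 weeks, with events spread evenly in time, the excess over 1 is multiplied by 27/52 = 0.52.

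| *v* | To week 27, *c* = 0.52 to 0.96 | To week 52, *c* = 0.52 to 0.96 |
|---|---|---|
| 0.5 | 1.47 to 1.87 | 1.24 to 1.45 |
| 0.7 | 1.20 to 1.37 | 1.10 to 1.19 |
| 0.9 | 1.05 to 1.10 | 1.03 to 1.05 |
| 1.0 | 1.00 | 1.00 |

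With *t* = 0.5 the week-27 ranges fall to 1.26 to 1.48, 1.11 to 1.21 and 1.03 to 1.05 for *v* = 0.5, 0.7 and 0.9. With *t* = 0 the ratio is 1.0 throughout. The documents give neither *v* nor *t*.

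**4. Appendix 2 against the text.** These two mismatches need no assumption:
- Section 7 starts collection at consent; the first mark in the row is at the first intervention session.
- Sections 3 and 5 have the week-39 call document potential serious events; the row is blank there.

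**The case against.** The case on the other side is substantial.

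- **No harms comparison is specified.** Section 8 contains none and leaves full detail to the analysis plan. Adverse-event handling follows a sponsor operating procedure that is not shown. This stands: the bias attaches to a comparison that may be made, not to one the protocol sets out. It does not remove the point, because the schedule fixes unequal collection and the DMEC sees the counts.
- **TAU is not silent between visits.** A reader might infer that TAU events are recorded only at research visits. The text does not support that. Section 7 covers all participants from consent. Section 6 offers everyone a telephone contact within 48 hours of assessments and gives them the researchers' contact details, and the week-39 call covers both arms. Because both arms have these contacts, they narrow the gap without closing it.
- **Important harms have an arm-neutral source.** LIFE rates symptom severity week by week through blinded assessors. Inpatient days are captured in both arms through LIFE and the service use interview (section 2). This stands. A reader might infer that a benefit on symptom worsening would be hidden, but worsening is measured independently of therapists. Deaths and admissions should also be less exposed.
- **The recording rule is neutral in itself.** Recording by whoever identifies the event favours neither arm in its wording. The imbalance comes from Appendix 2 combined with the absence of a therapist in TAU; the rule does nothing to offset it.
- **Limiting a comparison to common contacts could understate harm under CBT.** This is fair, and is met by showing all events as well.

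**Conclusion.** The plan builds in unequal opportunity to record adverse events: up to 29 scheduled occasions against 3, or about 17 against 3 at the feasibility mean. Any comparison by arm is therefore open to ascertainment bias, and the expected direction is against CBT. The exposure lies mainly in non-serious events such as self-harm without admission.

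It would go too far to say that the comparison is biased or that CBT will look more harmful. With equal true rates the illustrative ratio to week 27 runs from 1.0 (visits capture everything) to about 1.9 (visits capture half, a session almost every week, and therapists find 90% of what visits miss). A ratio of 2.0 at half capture would need a session in every week and a therapist who misses nothing. All of these capture rates are assumptions.

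The two mismatches between Appendix 2 and the text hold whatever the capture rates are. Nothing here affects the sample size, the significance level or the co-primary analyses.

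**What to change.** 1. Ask one identical structured adverse-event question in both arms at weeks 17, 27 and 52, and a serious-event question at week 39, each covering the whole period since the last contact.
2. Add a field to the Adverse Events Report Form for the source of the event (shared study contact, therapist or other).
3. Base any between-arm comparison, including tables by arm for the DMEC, on events found at the shared contacts. Show beside it all events by arm, with events known only through the therapist identified, so that none is dropped.
4. Reconcile the adverse-event row of Appendix 2 with section 7 (collection from consent) and with sections 3 and 5 (serious events documented at week 39).

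Expedited reporting of serious events is unchanged. The cost is one form field, a second safety table and a correction to the appendix.

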8. STATISTICS & DATA ANALYSIS

MAIN TRIAL DATA ANALYSIS

All comparative analyses will be 'as randomised', where participants are analysed according to the group they were randomised to, regardless of what treatment they received. Complete details of analyses will be included in a Statistical Analysis Plan which will be finalised and approved by the Trial Steering Committee prior to database lock and prior to any analysis.

Co-primary outcomes

The primary analyses for each of the co-primary outcomes (mean 4-week PSR for LIFE depression score and for LIFE mania score at 27-week follow-up) will use ANCOVA, with adjustment for the stratification factors (site and BAR group) and the baseline PSRs for depression and mania and prior CBT (yes/no). Missing data will be explored; for each co-primary, if less than 15% are missing, and less than 10% differential missing data, then case analysis (CCA) will be used, otherwise it will be multiple imputation by chained equations (MICE) [94] assuming that the data are 'missing at random'. Tests will use a 2.5% significance level and two-sided 97.5% confidence intervals (CIs) will be presented.

Moderator: We will explore BAR group (I, II or II) and prior CBT (yes; no) as potential moderators by adding interactions with treatment arm to the primary outcome models.

Mechanisms: We will evaluate this using causal inference methods for mediation [95] using an instrumental variables approach (via two-stage least squares) to estimate the indirect effect of CBT_{BAR} on each of LIFE mania and LIFE depression scores via the HAPPI total score at the preceding time-point (e.g. 17-week HAPPI for 27-week LIFE scores). The more complex causal model incorporating BC and ISS will be investigated using structural equation modelling. As a post-randomisation effect modifier, the impact of the number of CBT_{BAR} sessions attended will be assessed using principal stratification methods; other measures of intervention receipt, including antidepressant medication, will be considered in separate analyses.

Secondary outcomes

Secondary outcome measures (including the primary outcome measures at time-points other than 27-week) will be analysed using generalised linear models, with link function appropriate to the type of data, adjusted for stratification factors and the baseline value of the outcome measure (where applicable).Time to events (transition to first episode (hypo)mania and recovery from BAR symptoms) will be analysed using a Cox proportional hazards model, adjusted for stratification factors. Tests will use a 5% significance level and two-sided 95% CIs will be presented.

Sensitivity analysis

The alternative method to that used in the primary analysis will be used as a sensitivity analysis (MICE if CCA, or vice versa). Sensitivity analyses will also include the addition of a random therapist effect in a partially-nested model (clustering by therapist in the CBT_{BAR} + TAU arm but no clustering in the TAU arm). A further sensitivity analysis will use longitudinal mixed-effects model incorporating all follow-up time-points (as factors), fitted using maximum likelihood, accommodating the within-participant correlation over time with an unstructured covariance matrix and including stratification factors and the baseline PSRs for depression and mania as covariates.

QUALITATIVE ANALYSIS

Data will be analysed using thematic analysis [96], which provides an accessible and flexible approach, resulting in a rich account of qualitative data. The data generation and analysis will be conducted with leadership and ongoing involvement from individuals with personal experience of the provision of the receipt of this treatment and/or the experience of BAR mood experiences. This involvement is expected to enhance the study during the conduct and analysis of all interviews. We will take a critical realist position, and data will be coded at a manifest level (i.e., analysing only the immediate meaning of participants' language) to produce an accessible body of coded data from which meaningful thematic representations of participants' perspectives can be reported. All semi-structured interviews will be transcribed verbatim and coded systematically and iteratively within NVivo qualitative data analysis software (Version 11, 2016).

In order to achieve our objectives to explore mechanisms, participant interviews will be analysed to investigate the mechanisms by which the intervention is perceived to operate. Here we will employ an inductive approach whereby the researchers will not impose a pre-existing theoretical framework but will seek to identify and code

data that offer relevant information about how participants experience or perceive the intervention to have impacted on their mood, behaviours and symptoms and draw patterns across participants' experiences. The analysis will be conducted by qualitative researchers with lived experience and will follow the steps of Braun and Clarke [97]. Regular analysis meetings with the wider multidisciplinary research team which leads to further develop emerging thematic and conceptual outputs.

In order to explore implementation, stakeholder interviews will also be analysed inductively following the 7 steps of Braun and Clarke's approach, to examine the potential barriers and solutions to implementing the intervention into routine care and services. Regular analysis meetings will be key, not only to support the development of the emerging analysis, but also to ensure that valued that may be relevant to trial participant recruitment, are transmitted to the teams as a whole as quickly as possible Member checking will be conducted to ensure the trustworthiness of the final analysis [98].

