In addition to the main trial, we will also be conducting qualitative interviews/focus groups to understand the perceived mechanisms of change for the participants offered the CBT_{BAR} (mechanistic objective), as well as the implementation of CBT_{BAR} in NHS services (implementation objective).

We will recruit two groups of up to 25 participants. The first group will be participants from the treatment arm across of 5 sites. The 2nd group will be key stakeholders including health professionals, service providers, commissioners, service providers/leads, clinicians, and service users.

Sampling will be purposive. For the implementation group we will be recruiting participants who received the CBT_{BAR}, their family members, and a mix of health professionals including those delivering the therapy, those who are experienced in delivering CBT, and commissioners. For the perceived mechanism of change group we will be recruiting participants who scored differently on the therapeutic alliance measure, who have varying mood experiences following the intervention (as measured by the SCID-5 + PSR's (SCID LIFE)), and who have varying change in their appraisals (as measured by the HAPPI). For both the implementation and perceived mechanism of change interviews with our service user participants, we will seek a diverse & inclusive sample (e.g. ethnicity, socioeconomic status, gender), level of engagement in therapy, and non-responders. We will be considering what services the BAR group of young people are currently accessing e.g. primary care and take into account the different service set ups across the multiple sites taking part in this trial.

Participants who take part in a qualitative interview/focus group will receive £20 reimbursement for their time.

Sample Size

Sample size: quantitative work

Whilst we plan to include LIFE depression and LIFE mania 4-week average PSR scores as co-primary outcomes, overall symptom severity of depression is greater compared with mania in this population, as is its standard deviation [80]. Although it may be argued that a minimally clinically important difference (MCID) in LIFE PSR mania score is somewhat smaller than the MCID for the PSR depression score, the relative difference will be smaller than that for the SD. This means that the Standardised Effect Size (SES) will be smaller for depression than that for mania and, therefore, that the sample size to detect the MCID will be greater for depressed mood

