than for mania. On the LIFE PSR, our eligible population will score at the higher end of the subthreshold range (3-4) as those scoring 5-6 will confer research diagnostic criteria and therefore not meet the inclusion criteria for the trial; based on our pilot trial (mean baseline BDI-II score of 37.9), participants will tend to be towards the upper end of the subthreshold range (i.e. mean around 3.75). Button [81] reported that a MCID for the BDI-II is around 17-18%; given that we expected similar sensitivity for the mean LIFE depression PSR scores as would be the case for BDI-II, a difference of around 0.5 points (0.18*[3.75-1]=0.50 (to 2 d.p.)] on the PSR for LIFE depression in order to indicate that CBT_{BAR} is having an important effect.

To detect a between-group mean difference of 0.5 points (SD=1.3 points [80]) on the mean 4-week PSR for LIFE depression score at 27-weeks follow-up we require 286 participants with outcome data to achieve 90% power, using an ANCOVA (with 2.5% two-sided significance level), assuming a conservative correlation of 0.4 between baseline and 27-week scores [82]. Inflating the sample size to allow for a conservative 15% attrition (attrition was 13% in our feasibility trial, 57) requires a target to randomise of 338 participants (approx. 68 per site). This sample size will provide greater than 90% power to detect a rather more conservative MID on LIFE PSR for mania (e.g. equating to 98.5% to detect a target effect of 0.25 points [estimated within-group SD=0.5 points]) [80]. In each case, power will be increased due to the (multiple) correlation between outcome and the full set of explanatory variables adjusted for in the model. We have not allowed for a random therapist effect in our sample size calculation as the effect on depression outcome (BDI-II) in our pilot trial was 0, although the confidence interval was wide; we will, however, include the addition of a random therapist effect amongst our sensitivity analyses.

Assuming a standardised effect size of the intervention on the HAPPI of 0.4, 286 participants with mediator and primary outcome data will also allow for 88.5% power for estimation of an indirect effect of 40% via the putative primary mediator (HAPPI), or 83.5% power for the estimation of a 30% indirect effect, based on a total effect on the intervention of the MCID (i.e. 0.5) (with a 2.5% significance level, estimated using the R package medssp, based functions provided in Vittinghoff and Neilands [83]

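### Testing each co-primary outcome at a flat 2.5% is valid, but a Holm step-down at the same implied 5% family-wise error never rejects less and could add up to about 4 points of power for depression

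*Protocol*

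**What the plan says.** Section 3 (Sample size: quantitative work) introduces the two outcomes: "Whilst we plan to include LIFE depression and LIFE mania 4-week average PSR scores as co-primary outcomes". It sizes the trial on depression. The target is stated as "To detect a between-group mean difference of 0.5 points (SD=1.3 points [80", and the requirement is "we require 286 participants with outcome data to achieve 90% power, using an ANCOVA (with 2.5% two-sided significance level". The calculation takes 0.4 as the correlation of the baseline score with the 27-week score. After 15% attrition this "requires a target to randomise of 338 participants". For mania the same number is said to give power "equating to 98.5% to detect a target effect of 0.25 points [estimated within-group SD=0.5 points".

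Section 8 (Co-primary outcomes) fixes the decision level: "Tests will use a 2.5% significance level and two-sided 97.5% confidence intervals". Section 8 (Secondary outcomes) uses 5% and 95% intervals. No step-down or passing-on of error between the two co-primaries is described. The protocol does not name a multiplicity method, state a family-wise level, or say whether success needs one outcome or both.

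**The concern.** Halving the level for two outcomes, while secondary outcomes keep 5%, looks like a Bonferroni split of 5%. Under such a split, once one null hypothesis is rejected at 2.5%, the other can be tested at 5% without the family-wise error exceeding 5%. A flat split leaves that allowance unused.

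The unused part is largest in the scenario the protocol plans for. Depression is the limiting outcome and drives the sample size, while mania is expected to succeed nearly always. With mania clearly positive and a depression p-value between 0.025 and 0.05, the flat rule does not call depression significant, although 5% family-wise control would allow it.

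**Working it through.** **Inputs.** From Section 3: depression difference 0.5, SD 1.3; mania difference 0.25, SD 0.5; correlation 0.4 (stated for the depression calculation); 286 analysed; level 2.5% two-sided. Equal allocation (143 per arm) is inferred from the 169 of 338 expected to receive CBT in Section 12. The correlation between the two test statistics is not given; I assumed a range of -0.3 to 0.6.

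**Reproducing the plan.**
- ANCOVA SD = 1.3 x sqrt(1 - 0.4²) = 1.191.
- Total N = 4 x [1.191 x (2.241 + 1.282) / 0.5]² = 282 by normal approximation, against 286 stated.
- Attrition: 143 / 0.85 = 168.2, so 169 per arm and 338 in all, as stated.
- Standard error for depression = 1.191 x sqrt(2/143) = 0.141, so the expected z is 0.5 / 0.141 = 3.548. Power at 2.5% = Φ(3.548 - 2.241) = 90.4% (90.2% by the t distribution).
- Mania power at 2.5% is 99.1% with the 0.4 adjustment and 97.7% without; the stated 98.5% lies between.

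**Depression power under Holm.** At 5%, depression power is Φ(3.548 - 1.960) = 94.4%. Holm gives depression the 5% level only when mania passes at 2.5%. With independent tests:

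Holm power = 0.904 + (0.944 - 0.904) x (mania power at 2.5%)

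Using unrounded values (0.9044 and 0.9439):
- planned mania effect: 0.9044 + 0.0395 x 0.991 = 94.4%;
- half the planned effect (0.125; mania power 52.6%): 0.9044 + 0.0395 x 0.526 = 92.5%;
- no mania effect: 0.9044 + 0.0395 x 0.025 = 90.5%.

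**Varying the correlation between tests.** Bivariate normal simulation, 4 million draws per setting, correlations -0.3, 0, 0.3 and 0.6, with the mania SD adjusted for the 0.4 correlation:

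| True mania effect | Depression, flat | Depression, Holm | Gain (points) | Both, flat | Both, Holm |
|---|---|---|---|---|---|
| 0.25 (planned) | 90.4-90.5% | 94.3-94.4% | 3.8-3.9 | 89.6-90.1% | 94.0-94.1% |
| 0.125 (half) | 90.4-90.5% | 91.0-93.2% | 0.6-2.8 | 45.7-51.5% | 58.5-62.3% |
| 0 | 90.4-90.5% | 90.5-90.6% | 0.1-0.2 | not applicable | not applicable |

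Without the adjustment for mania, the planned-effect gain is 3.6 to 3.9 points. The chance of showing at least one outcome is identical under both rules in every setting.

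**Error control.** Under the global null, Holm's simulated family-wise error is 4.5% to 5.0%. With a depression null and a strong mania effect (test correlation 0.3) it is 5.0%; with a mania null and the planned depression effect it is 4.4% to 4.8%.

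**Which depression results change.** p = 0.05 corresponds to 1.960 x 0.141 = 0.28 points, and p = 0.025 to 2.241 x 0.141 = 0.32 points. The verdict therefore changes only for observed differences of about 0.28 to 0.32, or 55% to 63% of the 0.5-point difference, and only when mania is significant at 2.5%.

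**The case against.** The flat rule contains no mistake. Sample size, tests and intervals all use 2.5%, the 90% target for depression is met under that rule, and each outcome gets one interval that agrees with its test and has simultaneous coverage. Keeping test and interval aligned is a legitimate reason to choose it. All of this stands.

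The 4 points also need mania to succeed. The 0.25-point mania effect is half an SD and is offered only as an example. Its SD comes from a trial of psychoeducation or CBT in bipolar disorder, whereas this trial excludes anyone with a past manic episode of a week or more. This stands too, so the gain must be stated as conditional.

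The depression results that change verdict lie below the protocol's important difference. That limits their clinical weight. It does not favour the flat rule, whose own significance boundary (0.32) is also below 0.5.

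A reader might infer more: that the flat split is an error, that 4 points are lost whatever happens, or that the plan obliges the trial to declare depression negative at p = 0.03. The documents support none of these. The split controls error, the gain shrinks to almost nothing without a mania effect, and no success or declaration rule is written down. If success required both outcomes, no split would be needed and Holm would be the wrong remedy.

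A step-down could also appear in the statistical analysis plan, which is not shown. The protocol itself fixes 2.5% for each test.

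**Conclusion.** This is a cheap improvement, not the correction of an error. At the same implied 5% family-wise level, Holm never rejects less than the flat 2.5% rule. With 286 analysed and a correlation of 0.4, depression gains about 4 points of power under the planned mania effect, about 1 to 3 at half that effect, and about 0.1 with none. Power to show both outcomes rises from about 90% to 94% under the planned effects.

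The conclusion rests on two inferences: that the family-wise level is 5%, taken from 2 x 2.5%, and that each outcome is meant to be concluded on separately. The size of the gain rests on the protocol's planning values and on the assumed range of correlation between the tests.

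**What to change.** Before any analysis, state how the two outcomes lead to a conclusion. If each is to be concluded on separately, add to Section 8 wording such as: the smaller of the two co-primary p-values is tested at 2.5% two-sided; if it is significant, the other is tested at 5% two-sided (Holm).

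Keep N = 338 and its sizing at 2.5%, which is conservative under Holm. Keep the 97.5% intervals as simultaneous intervals, show a 95% interval beside the outcome tested second, and say that the Holm test decides.

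The change needs no further participants or data. Its one real downside is in reporting: for an outcome that passes only at the 5% step, the 97.5% interval includes zero while the test rejects, and this must be explained. It has to be specified in advance to be credible.
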